3.0 Background

- 3.1 Point-of-Care Ultrasonography (POCUS) has been recognized as a powerful tool to evaluate critically ill patients. Using gastric ultrasonography, we can evaluate gastric volume and the types of contents as well as gall bladder size. The cross-sectional area of the gastric antrum is used to calculate the gastric volume. The full stomach state in pediatric patients scheduled for elective surgery is low at only 0-1%. However, it is unknown how lack of appropriate NPO time affects gastric volume and contents as well as gall bladder size. The gallbladder stores bile and starts to empty after the presence of fatty food in duodenum. Gallbladder emptying also

requires relaxation of the sphincter of Oddi, which may be disturbed by opioids. Therefore, it may be useful to evaluate patient NPO status. The diameter of great vessels has been used to evaluate patient volume status in pediatric patients.

- 3.2 Point-of-care gastric ultrasound had a sensitivity of 1.0 and a specificity of 0.975 to detect a “full stomach”. ¹ Using point-of-care gastric ultrasound, a previous study reported that 0-1 % of the healthy pediatric patients scheduled for elective surgery were at risk of pulmonary aspiration ^{2 3} However, 35 % of the adult patients scheduled for unplanned surgery had a full stomach even after ≥ 6 hours of NPO time ⁴ The normal gallbladder sizes in healthy children has been evaluated after fasting in previous report. ⁵ There is no article which reports the relationship between NPO state and gallbladder size.
- 3.3 Rapid sequence induction (RSI) is widely used to avoid pulmonary aspiration during anesthetic induction. However, RSI is the risk factor for oxygen desaturation and other airway complications when compared to standard anesthetic induction techniques. The current study will help identify which trauma patients are truly at risk for aspiration and therefore require RSI.

4.0 Study Endpoints

- 4.1 The primary study endpoint is the number (percentage) of patients in the urgent, emergent group with a full stomach state as assessed by gastric volume and contents despite an appropriate NPO time.
- 4.2 The secondary endpoint will be to determine gall bladder size between fasted patients undergoing elective versus urgent/emergent surgery. The other endpoint will be to evaluate the preoperative volume status.

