2.0 Objectives

- 2.1 The primary objective of this study is to evaluate gastric volume and contents as well as gall bladder size in patients scheduled for routine, urgent, and emergency surgery.
- 2.2 The hypothesis is that patients with stress, pain and opioid administration will have delayed gastric emptying and therefore a larger gastric fluid volume than those scheduled for elective surgery. The patients who have an appropriate NPO time will have a larger gallbladder size than the patients with shorter NPO time.

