6.0 Procedures Involved*

6.1 This is a prospective observational study that will be conducted in 300 patients, ranging in age from 2 to 18 years who are scheduled for routine, urgent or emergent surgeries. There will be no change in clinical practice regarding choice of anesthetic technique as a result of this research study. Before surgery in the pre-operating area, the ultrasonographer will evaluate the gallbladder size and volume. Procedure time will be recorded for the ultrasonography. Demographic data, including age, sex, height, weight, nil per os time, preoperative symptoms, administered opioids, and types of the surgery will be recorded.

6.2

Ultrasound protocol

All ultrasound scans will be performed by study investigators by using Sonosite X-porte (Sonosite Inc. USA) machine and 3-8 MHz curved linear probe with abdominal setting. The investigators have enough experiences of POCUS.

All patients will be lying supine, followed by RLD position. Patients were placed in the supine position, followed by the right-lateral decubitus (RLD) position. In cases where it is not feasible to place the patient in the right lateral decubitus position, the patient can be placed in a 45 degree head up position with a bump placed under the left hip. The gastric antrum is identified in a sagittal plane between the left lobe of the liver and the pancreas at the level of the descending aorta and supra mesenteric artery or inferior vena cava, as previously reported.⁶ One video clip will be recorded for each patient in the supine and RLD positions. The qualitative measurements (empty versus nonempty) will be reported to the attending anesthesiologist. The quantitative measurements will be performed at later time. The quantitative exam is performed using the cross-sectional area of the gastric antrum. The CSA of the antrum will be measured with a free-tracing method to follow the outer margin of the antrum corresponding to the serosa.⁷ The gastric volume will be calculated using the following formula.⁸

$$\text{Gastric volume (ml.kg}^{-1}\text{)} = [-7.8 + 0.035 \times \text{CSA (mm}^2\text{)} + 0.127 \times \text{age (months)}]/\text{body weight (kg)}.$$

The qualitative measurements will be performed using 3-point grading scale.⁹

Grade 0: no fluid visible in the antrum in either the supine or RLD position.

Grade 1: antral fluid visualized only in the RLD position.

Grade 2: antral fluid visualized in both the supine and RLD position.

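### The only gallbladder endpoint (4.2) compares surgical urgency among fasted patients, so no endpoint tests the NPO-time hypothesis stated in 2.2

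*Combined protocol and SAP*

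**What the plan says.** Section 2.1 sets out to "evaluate gastric volume and contents as well as gall bladder size in patients scheduled for routine, urgent, and emergency surgery". Section 2.2 gives the gallbladder hypothesis: "The patients who have an appropriate NPO time will have a larger gallbladder size than the patients with shorter NPO time". The Background treats this as an open question. Section 3.1 says "it is unknown how lack of appropriate NPO time affects gastric volume and contents as well as gall bladder size", and 3.2 adds: "There is no article which reports the relationship between NPO state and gallbladder size".

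Section 4.2 then defines the gallbladder endpoint: "The secondary endpoint will be to determine gall bladder size between fasted patients undergoing elective versus urgent/emergent surgery". The other two endpoints are full stomach (4.1) and preoperative volume status (4.2).

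Section 6.2 computes gallbladder volume as a prolate ellipsoid, 0.52 × L × W × W. Section 17.1 lists generic bivariate tests and does not mention the gallbladder.

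**The concern.** The hypothesis varies fasting. The endpoint restricts to fasted patients and varies surgical urgency. If 4.2 is followed as written, the study produces no prespecified estimate for the gallbladder question it calls unanswered. A later comparison by NPO time would rest on a definition of appropriate NPO time, and a choice of reported analysis, made once the data are in hand.

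The urgency comparison cannot stand in for the NPO comparison. Section 3.1 gives two separate influences on the gallbladder. Feeding is one: "The gallbladder stores bile and starts to empty after the presence of fatty food in duodenum". Opioids are the other, because emptying "requires relaxation of the sphincter of Oddi, which may be disturbed by opioids". A difference by urgency among fasted patients could reflect opioids, and would say little about time since intake.

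The second matter is body size. Gallbladder volume is absolute, the children range from 2 to 18 years, the groups are not randomised, and no adjustment is planned.

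**Working it through.** **1. Hypothesis and endpoint side by side.**

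| Element | Hypothesis (2.2) | Endpoint (4.2) |
|---|---|---|
| Contrast | Appropriate v shorter NPO time | Elective v urgent/emergent surgery |
| Patients needed | Both NPO groups | Fasted patients |
| Expected direction | Larger with appropriate NPO time | None given |
| Measure | Gallbladder size | Gallbladder size |

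Only the measure agrees. If fasted in 4.2 were read loosely, so that it covered every preoperative patient, the short-NPO patients would stay in, but the contrast would still be urgency.

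**2. The other endpoints.** Section 4.1 counts full stomachs among urgent and emergent patients with appropriate NPO time. The remaining endpoint is volume status. Neither has a gallbladder element. The primary outcome in 17.1 is the proportion with a full stomach. So 0 of 3 listed endpoints carry the 2.2 gallbladder contrast.

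**3. Could the data answer the question?** Yes. Section 10.2 admits ASA 1-3 patients aged 2-18 and excludes only previous upper gastrointestinal surgery; it sets no fasting requirement. Section 6.1 provides the variables: "Demographic data, including age, sex, height, weight, nil per os time, preoperative symptoms, administered opioids, and types of the surgery will be recorded".

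**4. Is appropriate NPO time defined?** The term is used in 2.2, 3.1 and 4.1 without a cut-off. The 6 hours in 3.2 describes a cited adult study and is not presented as this study's rule.

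**5. Body size.** The gastric formula in 6.2 divides by body weight; the gallbladder formula does not. For independent continuous variables 17.1 names the t-test and the Wilcoxon rank-sum test, with no covariates. If the groups differ in size, an unadjusted comparison is confounded. If they do not, adjustment would still gain precision to the extent that size explains gallbladder volume. The documents give no size distribution by group, so the amount cannot be derived.

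**6. Precision of the missing contrast (illustration only).** The plan has no figure to reproduce for any gallbladder comparison. Its one design figure is 3 × 100 = 300 (12.1), given without power, effect size or SD. The number of short-NPO patients is not stated; 30 of 300 is assumed here, with 80% power and two-sided 5%.

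- Formula, in residual SD units: detectable difference = (1.960 + 0.842) × √(1/n₁ + 1/n₂) / √(1 − R²). R² is the share of variance in the short-NPO indicator explained by the adjustment terms.
- Unadjusted (R² = 0): 2.802 × √(1/30 + 1/270) = 2.802 × 0.1925 = 0.54 SD.
- Adjusted for urgency, all 30 in one group of 100: the group proportions are 0.30, 0 and 0, with mean 0.10. Between-group variance = (0.20² + 0.10² + 0.10²)/3 = 0.02. Total variance = 0.10 × 0.90 = 0.09. R² = 0.02/0.09 = 0.222. Detectable difference = 0.539/√0.778 = 0.61 SD.

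Fewer short-NPO patients would make this worse. An opioid term correlated with short NPO time would also widen it. A weight term would narrow it by lowering the residual SD, unless weight is itself correlated with NPO time. These figures apply to a two-group NPO indicator, not to NPO time entered as a continuous variable.

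**The case against.** The best defence is that 2.2 already states the contrast and its direction, that 17.1 lists two-sample tests that fit it, and that every needed variable is collected. A reader might infer that the whole NPO comparison would be invented after the fact, or that the study cannot address it. Neither follows. What is missing is narrower: an endpoint that includes the short-NPO patients, and a definition that separates the two groups. That much stands, because generic tests do not make a comparison an endpoint, and 4.2 points to a different one.

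A reader might also infer that the planned gallbladder comparison is biased by body size. The documents do not show that the groups differ in age or weight, so this is a possibility of unknown size and adjustment is a precaution. Section 17.1 never names the gallbladder, and 2.2 and 4.2 speak of size rather than volume. Volume is taken as the measure here because it is the one for which 6.2 gives a formula.

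Finally, the added analysis may be imprecise, and the sponsor could reasonably prefer to drop the hypothesis. That is a legitimate way to remove the inconsistency. Leaving 2.2 and 4.2 as they stand is not.

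**Conclusion.** The mismatch between 2.2 and 4.2 is established from the text and depends on no numerical assumption: none of the three endpoints tests the stated gallbladder hypothesis, and the natural reading of 4.2 removes one of the two groups it needs. It should be corrected before analysis. It concerns a secondary endpoint and does not by itself affect the full-stomach endpoint in 4.1. The body-size point is conditional and of unknown amount. The 0.54 and 0.61 SD figures rest on an assumed 30 short-NPO patients and only indicate how precise the missing comparison might be.

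**What to change.** 1. Reword 4.2 as: *Gallbladder volume in patients with appropriate versus shorter NPO time, among all enrolled patients; additionally, elective versus urgent/emergent among patients with appropriate NPO time.*
2. Before analysis, state the study's own definition of appropriate NPO time, and use the same definition in 4.1 and 4.2.
3. Add to 17.1 a linear regression of gallbladder volume on the appropriate/shorter NPO indicator, adjusted for weight, urgency group and opioid use. Add a weight-adjusted elective versus urgent/emergent comparison among fasted patients.
4. Report the number of short-NPO patients overall and by urgency group, and the number of missing gallbladder measurements by group.

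If the sponsor does not intend to study NPO time, the alternative is to align 2.2 with 4.2 and drop the NPO-gallbladder hypothesis.

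The cost is wording in 4.2 and 17.1 and one definition, using variables already recorded, with no extra scans or patients. There are two consequences to accept openly. Recruitment is fixed by urgency, so the number of short-NPO patients is not controlled and the NPO estimate may be imprecise. The definition of appropriate NPO time also fixes who counts in primary endpoint 4.1, so it should be settled with that endpoint in view.

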5.0 Study Intervention/Investigational Agent

- 1.1 The only novel intervention is the use of ultrasound to evaluate gastric volume and contents, gall bladder size, and diameter of great vessels. Ultrasound is a non-invasive device, used commonly in the perioperative setting for placement of vascular access and regional anesthesia. There will be no change in anesthetic care for the study. There is no risk added by the study and the use of ultrasound.
- 5.1 The only interventions being used that is not normally used in general clinical practice is ultrasonography. The technique is non-invasive and poses no risk. Ultrasonography will be performed by an

anesthesiologist who has significant experience with Point-of-Care Ultrasound.

6.0 Procedures Involved*

6.1 This is a prospective observational study that will be conducted in 300 patients, ranging in age from 2 to 18 years who are scheduled for routine, urgent or emergent surgeries. There will be no change in clinical practice regarding choice of anesthetic technique as a result of this research study. Before surgery in the pre-operating area, the ultrasonographer will evaluate the gallbladder size and volume. Procedure time will be recorded for the ultrasonography. Demographic data, including age, sex, height, weight, nil per os time, preoperative symptoms, administered opioids, and types of the surgery will be recorded.

6.2

Ultrasound protocol

All ultrasound scans will be performed by study investigators by using Sonosite X-porte (Sonosite Inc. USA) machine and 3-8 MHz curved linear probe with abdominal setting. The investigators have enough experiences of POCUS.

All patients will be lying supine, followed by RLD position. Patients were placed in the supine position, followed by the right-lateral decubitus (RLD) position. In cases where it is not feasible to place the patient in the right lateral decubitus position, the patient can be placed in a 45 degree head up position with a bump placed under the left hip. The gastric antrum is identified in a sagittal plane between the left lobe of the liver and the pancreas at the level of the descending aorta and supra mesenteric artery or inferior vena cava, as previously reported.⁶ One video clip will be recorded for each patient in the supine and RLD positions. The qualitative measurements (empty versus nonempty) will be reported to the attending anesthesiologist. The quantitative measurements will be performed at later time. The quantitative exam is performed using the cross-sectional area of the gastric antrum. The CSA of the antrum will be measured with a free-tracing method to follow the outer margin of the antrum corresponding to the serosa.⁷ The gastric volume will be calculated using the following formula.⁸

$$\text{Gastric volume (ml.kg}^{-1}\text{)} = [-7.8 + 0.035 \times \text{CSA (mm}^2\text{)} + 0.127 \times \text{age (months)}]/\text{body weight (kg)}.$$

The qualitative measurements will be performed using 3-point grading scale.⁹

Grade 0: no fluid visible in the antrum in either the supine or RLD position.

Grade 1: antral fluid visualized only in the RLD position.

Grade 2: antral fluid visualized in both the supine and RLD position.

“Full stomach is defined by the visualization of solid contents or frost-grass pattern and/or by a calculated gastric fluid volume $>1.5 \text{ ml.kg}^{-1}$.

The gallbladder size and volume will be evaluated as previously reported.⁵

The gallbladder volume was calculated as following formula.

Volume = $0.52 \times L$ (the greatest length) $\times W$ (anterior posterior dimension) $\times W$ (transverse width)

B and C are assumed to be equal.

[figure not shown]

FIGURE 1. Method of sonographic measurement of gallbladders. The gallbladder volume was measured using the prolate ellipsoid volume formula: $V = 0.52 \times L \times W \times W$. A is the greatest length (L), B is the anteroposterior dimension (W) and C is the transverse width (W). B and C were assumed to be equal.

The diameter of great vessels will be measured in supine position.

Demographic data, including age, sex, height, weight, nil per os time, preoperative symptoms, administered opioids, and types of the surgery will be recorded.

6.3 There are no foreseeable risks associated with the use of ultrasound.

6.4

Ultrasound data will be stored in the ultrasound machine. The research team will transmit the data to the password-secured server and store as MP4 file and JPEG file. The data will then be deleted from the ultrasound machine.

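### Is the primary endpoint left undefined because the plan does not name the scan position for the antral area or say how to handle patients who cannot be turned?

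*Combined protocol and SAP*

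**What the plan says.** The primary endpoint (section 4.1) is the percentage of urgent and emergent patients with a "full stomach state as assessed by gastric volume and contents despite an appropriate NPO time". The end of section 6.2 gives the definition: "Full stomach is defined by the visualization of solid contents or frost-grass pattern and/or by a calculated gastric fluid volume" above 1.5 ml/kg. Either limb is enough.

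On positions, section 6.2 starts with the rule "All patients will be lying supine, followed by RLD position". It then makes an exception where RLD is not feasible: "the patient can be placed in a 45 degree head up position with a bump placed under the left hip". The recording sentence is "One video clip will be recorded for each patient in the supine and RLD positions".

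On measurement, the same section says "The quantitative measurements will be performed at later time" and "The quantitative exam is performed using the cross-sectional area of the gastric antrum". The area is traced along the outer margin of the antrum and entered, with age and weight, in a volume formula taken from reference 8. The formula has one CSA term and no term for position.

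The qualitative scale is defined by supine and RLD only, for example "Grade 1: antral fluid visualized only in the RLD position". For the great vessels, section 6.2 does name a position (supine). Section 17.1 has no rule for scans made in the fallback position.

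**The concern.** Three silences meet in one input to the primary endpoint. The formula needs one area, and the text does not say which position provides it. Clips are planned for two positions, while a third is allowed. The area is traced after the session, so only what was saved can be measured.

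Read literally, a patient who could not be turned has a supine clip and no RLD clip. If the formula is meant for the RLD area, the volume limb is then undetermined for that patient or is filled from another position. For a patient with no solid contents or frost-grass pattern, the volume limb alone decides the class. One analyst might drop the patient, another use the supine area, and a third use a 45-degree clip if one was kept.

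Dropping such patients could be selective. Section 3.3 looks to trauma patients, section 2.2 expects slower emptying with pain, and such patients might also be harder to turn. The documents do not say that they are.

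**Working it through.** The plan has no stated figure to reproduce here. Section 12.1 gives 100 patients per group with no power calculation. The check is therefore a reading of the text, followed by a bound on the possible effect.

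**1. What the text settles.** The formula comes by citation, so the position it was built for is a matter of looking up reference 8. That source is not available here, and nothing below assumes its answer. The fallback sentence directly follows the RLD instruction and applies only where RLD is not feasible, so it most naturally replaces the second scan. The recording sentence then describes the usual sequence. Section 6.4 stores the ultrasound data as video and image files without limiting them to two positions. This does not prove that a fallback clip is kept, but it weakens the inference that none is.

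**2. Could position matter for a single patient?** Setting the volume to 1.5 ml/kg and solving for the area gives

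CSA = (1.5 × weight + 7.8 − 0.127 × age in months) / 0.035.

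Weights are assumed.

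- Age 2 years, 12 kg: (18 + 7.8 − 3.048) / 0.035 = 650 mm². A 10–30% change in area (assumed) moves the volume by 0.19–0.57 ml/kg.
- Age 15 years, 55 kg: (82.5 + 7.8 − 22.86) / 0.035 = 1927 mm². The same change moves it by 0.12–0.37 ml/kg.

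A patient near the cut-off could therefore change class. The documents do not say how far the area differs between positions.

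**3. Bound on the primary percentage.** If the formula takes the supine area, the supine clip exists for everyone and the effect is zero. If it takes the RLD area, let f be the share of patients with an undetermined volume limb (assumed). Let p be the full-stomach proportion among the rest, and s the share of fallback patients already full by solids. Then

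lower limit = (1 − f)p + fs; upper limit = (1 − f)p + f; width = f(1 − s).

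With s = 0, the worst case:

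| f (assumed) | p = 35% (adult rate, section 3.2) | p = 10% (assumed) |
|---|---|---|
| 5% | 33.3–38.3% | 9.5–14.5% |
| 10% | 31.5–41.5% | 9.0–19.0% |
| 20% | 28.0–48.0% | 8.0–28.0% |

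**4. Against sampling error.** The width of the 95% interval is 2 × 1.96 × √(p(1 − p)/n).

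- n = 200 (urgent plus emergent): 13.2 points at 35% and 8.3 points at 10%.
- n = 100 (assumed, if the fasting restriction halves the group): 18.7 and 11.8 points.

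With s = 0 the bound's width equals f, so these widths are also the break-even shares: about 13% and 8% with 200 patients, 19% and 12% with 100. If half of full stomachs are full by solids (assumed; s = 0.175 at p = 35%), the first becomes 13.22 / 0.825 = 16.0%. Below these shares, sampling error is the larger uncertainty.

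**The case for a change.** The strongest case for a change is that the gap is real and cannot be repaired afterwards. The scan is made just before surgery, so a view not saved cannot be repeated under the same conditions. The position used is not among the data items listed in sections 6.1 and 6.2, so even the number of fallback patients may be hard to recover. The plan names a position for the great vessels, so the silence on the CSA is a true omission. A citation can say which position the formula needs, but it cannot supply an RLD clip for a patient who was never turned. If full stomachs are nearer 10% than 35%, a fallback share of about 8% is enough to match sampling error.

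All of that stands as a description of the text. It does not show a wrong result. The harm needs the formula to take the RLD area, the fallback to be fairly common, and many of those patients to have no solids and be misclassified. The documents establish none of these. Grade 1 adds little: it concerns visible fluid, is not part of the full-stomach definition, and does not show that the area differs enough to cross 1.5 ml/kg. The possible selection of trauma or pain patients is conjecture.

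The obvious remedies also gain little. An extra fallback clip would not be traced if the formula takes the supine area, nor if fallback patients are simply bounded under RLD. Reporting the percentage twice, with the volume limb counted as not exceeded and then as exceeded, is one option among several for a descriptive single-site study. It is least informative where the problem would be largest: at f = 20% with no solids, the two figures are 20 points apart.

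**Conclusion.** The plan leaves out a detail that competent analysts can fill. They would take the CSA position from the cited formula, treat the 45-degree scan as the stand-in for RLD, classify solids as usual, and state in the report which position was used and how many patients needed the fallback. That is ordinary reporting and needs no change to the plan.

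The effect is zero if the formula takes the supine area. If it takes the RLD area, the primary percentage is uncertain by at most f percentage points. With 200 patients, that exceeds the 95% interval only if f passes about 13% (at a 35% rate) or 8% (at an assumed 10%). These are worst-case limits that rest on an assumed f and on no fallback patient being full by solids. The documents show neither how often the fallback is used nor any direction of error, so no bias in the primary endpoint is established.

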1.0 Study Summary

Study Title	Ultrasonographic evaluation of gastric volume and contents before surgery in children
Study Design	Prospective, non-blinded observational study
Primary Objective	The primary objective of this study is to evaluate gastric volume and contents in patients who are scheduled for elective, urgent, and emergent surgery
Secondary Objective(s)	None
Research Intervention(s)/ Investigational Agent(s)	There will be no change in anesthetic management or use of investigational agents.
IND/IDE #	Not applicable
Study Population	Patients who are scheduled for elective, urgent or emergent surgery
Sample Size	300 (100 in each group)
Study Duration for individual participants	Less than 10 minutes
Study Specific Abbreviations/ Definitions	CSA=cross sectional area POCUS=Point-of-Care Ultrasound RSI=Rapid Sequence Induction RLD=right lateral decubitus

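### Masked reading is not specified for the full-stomach outcome, although the antral trace is already deferred and the clips are already stored

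*Combined protocol and SAP*

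**What the plan says.** Section 4.1 sets the endpoint: "The primary study endpoint is the number (percentage) of patients in the urgent, emergent group with a full stomach state", restricted to those with an appropriate fasting time. Section 17.1 also names the proportion with full stomach as the primary outcome. Section 6.2 defines full stomach by visible solid or frosted content and/or a calculated volume above 1.5 ml/kg.

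Both limbs depend on a reader. For the volume limb, "The CSA of the antrum will be measured with a free-tracing method to follow the outer margin of the antrum", and the timing is deferred: "The quantitative measurements will be performed at later time". The content limb is a visual judgement. At the bedside, "The qualitative measurements (empty versus nonempty) will be reported to the attending anesthesiologist".

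Section 1.0 describes a "Prospective, non-blinded observational study". Section 2.2 expects patients with stress, pain and opioids to have delayed emptying and "therefore a larger gastric fluid volume than those scheduled for elective surgery". The study records fasting time, symptoms, opioids and type of surgery (section 6.1).

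The images needed for later reading are already planned: "One video clip will be recorded for each patient in the supine and RLD positions". Section 6.4 moves them to a secured server as MP4 and JPEG files.

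**The concern.** A free-hand outline and a content call both leave room for judgement. A reader who knows that a child came for emergency surgery and received opioids also knows which answer section 2.2 expects. If that knowledge pushes readings upward in urgent and emergent patients, the section 4.1 percentage rises, and so does any contrast drawn with elective patients. Enrolling more patients would not reduce such an error, and a confidence interval would not show it.

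Scanning in the preoperative area cannot readily be masked. Reading afterwards can be, and this plan already separates the quantitative reading from the scan. What is missing is a statement of who reads and what is withheld from them.

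**Working it through.** **Is masking specified anywhere?** Four places bear on it.

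- Section 1.0 labels the whole study non-blinded.
- Section 6.2 has study investigators do the scanning and defers the trace, but it neither names the later reader nor withholds any data from that reader.
- Section 17.1 adds nothing on reading.
- Section 27.0 answers not applicable to the question on coding identifiable data. Its list of safeguards does mention an assigned code number with a separate link list, but tick marks are not visible in the text available.

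The supportable statement is that masking of the reader is not specified.

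**Is there a figure for differential reading error?** No. Section 3.2 quotes a sensitivity of 1.0 and a specificity of 0.975 for point-of-care gastric ultrasound. That is overall accuracy. It does not say how much readings change when the reader knows the group.

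**How far could over-tracing move the result?** This is an illustration, not an estimate.

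Inputs from the documents:
- volume (ml/kg) = [-7.8 + 0.035 × CSA (mm²) + 0.127 × age (months)] / weight (kg), with a cut-off of 1.5 (section 6.2);
- 100 urgent + 100 emergent = 200 patients (section 12.1);
- a true rate of 35%, taken from section 3.2: "35 % of the adult patients scheduled for unplanned surgery had a full stomach".

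Inputs assumed:
- a second true rate of 20%;
- age/weight of 24 months/12 kg, 120 months/32 kg and 216 months/65 kg;
- log-normal volume with log-SD 0.6 or 0.8;
- every urgent/emergent CSA over-traced by a factor k, with full stomach decided by the volume limb alone.

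Step 1. CSA at the cut-off = (1.5 × weight + 7.8 - 0.127 × age) / 0.035. For 24 months/12 kg this is (18 + 7.8 - 3.048) / 0.035 = 650 mm². The other two pairs give 1159 and 2225 mm².

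Step 2. True volume t that reads as 1.5 after over-tracing = (-7.8 + 0.035 × CSA at cut-off / k + 0.127 × age) / weight.
- k = 1.05: t = 1.410, 1.440, 1.443 ml/kg.
- k = 1.10: t = 1.328, 1.385, 1.391 ml/kg.

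Step 3. Read rate = 1 - Φ(z(1-p) + ln(t/1.5)/SD), where p is the true rate. The ranges run over the three age/weight pairs and both SDs. The half-width is 1.96 × √(p(1-p)/200).

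| True rate | Read, k = 1.05 | Shift (points) | Read, k = 1.10 | Shift (points) | 95% half-width, n = 200 |
|---|---|---|---|---|---|
| 20% | 21.4-23.0% | 1.4-3.0 | 22.7-26.2% | 2.7-6.2 | 5.5 |
| 35% | 36.8-38.9% | 1.8-3.9 | 38.5-42.8% | 3.5-7.8 | 6.6 |

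The 5% scenario stays below sampling error. The 10% scenario exceeds it only at its upper end (6.2 against 5.5; 7.8 against 6.6). That end comes from the smallest child with log-SD 0.6, applied as if every patient were that child. The half-widths would be wider once the endpoint is restricted to appropriate fasting time, because fewer than 200 patients would count.

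**The case against.** The strongest reply is that the design was disclosed as non-blinded, the operators are experienced, and every error rate above is assumed. On this view masked reading is good practice, but no flaw has been shown. Much of that stands: nothing here demonstrates a bias, and the plan does not contradict itself. Experience does not remove expectation, however, and the label in section 1.0 does not explain why a reading that is already deferred should be done with group, fasting and opioid data to hand.

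Three stronger readings are tempting and are not supported.

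- *The reader is unmasked.* A reader might infer this from the study-level label. Section 6.2 does not name the later reader, so the text shows only that masking is unspecified.
- *Masking would remove a known false-call rate*, for example the 2.5% implied by 1 - 0.975. That is a total error rate. Masking leaves ordinary error in place and removes only the part driven by knowing the group, for which there is no figure. No illustrative false-call rate for the content limb can therefore stand as the benefit of masking.
- *The comparison with elective patients would turn falsely significant.* Section 4.1 is a percentage within urgent and emergent patients and names no elective comparator. The hypothesis in section 2.2 concerns fluid volume rather than the full-stomach proportion.

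It is also fair to object that relying on clips alone could lose solid content seen live but not captured, and that falling back on the bedside call could itself differ by group. Both objections stand, and the fix allows for them.

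**Conclusion.** The point holds as a worthwhile, inexpensive improvement. The primary outcome depends on judgement in both limbs, the hypothesis has a direction, and no masking of the reader is specified. The likely direction is upward in urgent and emergent patients; the size is unknown.

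The worst-case illustration gives shifts of 1.4-3.9 points for a 5% over-trace and 2.7-7.8 points for a 10% over-trace, across true rates of 20% and 35%. These figures rest on assumed ages, weights, volume distributions and uniform over-tracing. They show what is possible, not what will happen, and they cover the volume limb only. A reader might infer that the bias generally outweighs sampling error; even on these assumptions it does so only at the extreme of the 10% case.

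Which scanning position's CSA enters the volume formula is a separate clarification, and this point does not depend on it.

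**What to change.** - Store the planned clips under a study code, with the link file kept separately.
- Have the existing investigators make both the CSA trace and the solid/frosted-content call from coded clips in random order, without group, fasting or opioid data and, where possible, not on scans they performed. Merge age and weight only after tracing.
- Define the primary outcome from these masked reads.
- Record the bedside solid/frosted call as its own field. Section 6.2 names only an empty/nonempty result for the bedside report.
- Add a sensitivity analysis that counts a patient as full stomach if either the masked read or the bedside call shows solid or frosted content.
- Report, by group, how many patients had inadequate clips or relied on the bedside call.
- Leave the bedside report to the anesthesiologist unchanged.

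The cost is file coding, one data field and one sensitivity analysis, with no extra scan. Some limits remain. Acquisition stays unmasked, a reader may recognise a scan or guess the group from posture, and content seen only live may be missed on the clip.
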